**Table 7. Potentially Significant Drug Interactions**

Drug Class	Product name
Antiangular	RANOLAZINE
Antiarrhythmics	BEPRIDIL
	LIDOCAINE (SYSTEMIC)
Anticancer agents	ABEMACICLIB
	CERITINIB
	DASATINIB
	ENCORAFENIB
	IBRUTINIB
	IVOSIDENIB
	NERATINIB
	NILOTINIB
	VENETOCLAX
	VINBLASTINE
	VINCRISTINE
Anticoagulants	WARFARIN
	RIVAROXABAN
Antidepressants	BUPROPION
	TRAZODONE
Antifungals	KETOCONAZOLE
	VORICONAZOLE
	ISAVUCONAZONIUM SULFATE
	ITRACONAZOLE
Anti-HIV protease inhibitors	AMPRENAVIR
	ATAZANAVIR
	DARUNAVIR
	FOSAMPRENAVIR
	INDINAVIR
	NELFINAVIR

PFIZER CONFIDENTIAL

CT24-WI-GL02-RF02 4.0 Non-Interventional Study Protocol Template For Secondary Data Collection Study

15-Jun-2022

Page 33 of 41

Drug Class	Product name
	SAQUINAVIR
	TIPRANAVIR
Anti-HIV	DIDANOSINE
	DELAVIRDINE
	EFAVIRENZ
	MARAVIROC
	NEVIRAPINE
	RALTEGRAVIR
	ZIDOVUDINE
Anti-infective	CLARITHROMYCIN
	ERYTHROMYCIN
Antimycobacterial	BEDAQUILINE
	RIFABUTIN
Antipsychotics	QUETIAPINE
Calcium channel blockers	AMLODIPINE
	DILTIAZEM
	FELODIPINE
	NICARDIPINE
	NIFEDIPINE
Cardiac glycosides	DIGOXIN
Endothelin receptor antagonists	BOSENTAN
Hepatitis C direct acting antivirals	ELBASVIR/GRAZOPREVIR
	GLECAPREVIR/PIBRENTASVIR
	SOFOSBUVIR/VELPATASVIR/VOXILAPREVIR
	OMBITASVIR/PARITAPREVIR/RITONAVIR AND DASABUVIR
HMG-CoA reductase inhibitors	ATORVASTATIN
	ROSUVASTATIN
Hormonal contraceptive	ETHINYLMESTRADIOL

Drug Class	Product name
Immunosuppressants	CYCLOSPORINE
	TACROLIMUS
	SIROLIMUS
Long-acting betaadrenoceptor agonist	SALMETEROL
Narcotic analgesics	FENTANYL
	METHADONE
Sedative/hypnotics	MIDAZOLAM (ADMINISTERED PARENTERALLY)
Systemic corticosteroids	BETAMETHASONE
	BUDESONIDE
	CICLESONIDE
	DEXAMETHASONE
	FLUTICASONE
	METHYLPREDNISOLONE
	MOMETASONE
	PREDNISONE
	TRIAMCINOLONE

**Table 8. [SAMPLE] Results Table**

	Treated COVID-19 patients (N = n)	Control Group	Untreated COVID-19 patients (N = n)
Baseline Variables			
1.0 Demographics			
1.1 Age	-		
1.2 Gender	-		
2.0 Clinical Characteristics	-		
2.1 Comorbidities (ICD-10)	-		
2.2 Vaccination Status (incl. date)	-		
2.3 Baseline Medication Usage	-		
2.4 COVID-19 Symptom (incl. date)	-		
2.5 COVID Diagnosis Date (index)	-		
Outcome Variables	-		
3.0 HRU	-		
3.1 Hospitalizations	-		
3.2 Outpatient Visits	-		
3.3 Emergency Room Visits	-		
3.4 Procedures	-		
3.5 Laboratory Tests (incl. COVID-Related)	-		
4.0 Medical Costs (incl. COVID-Related)	-		
4.1 Outpatient Costs	-		
4.2 Inpatient Costs	-		
4.3 Emergency Room Costs	-		
4.4 Ancillary Costs	-		
5.0 Pharmacy Costs (incl. COVID-Related)	-		

	Treated COVID-19 patients (N = n) Control Group Untreated COVID-19 patients (N = n)
6.0 Medication Usage (incl. written date of prescription and fill history)	-
6.1 Antibiotic	-
6.2 Antiviral (incl. Paxlovid™, COVID-19 monoclonal antibodies)	-
6.3 Antithrombotic	-
6.5 Anti-inflammatory (incl. steroids)	-

### ANNEX 3. IMMUNOCOMPROMISED ICD-10 CODE LIST

Participants will be identified as immunocompromised (IC) if they had  $\geq 1$  hospitalization or  $\geq 2$  outpatient visits on separate dates with an ICD-10-CM code on a healthcare claim indicating an IC condition or if they had usage of specific immunosuppressive medications during the 12-month baseline period.

The list of ICD-10-CM codes used to identify IC cases by diagnosis and list of immunosuppressive medications are shown below in Table 9

**Table 9. ICD-10 Code List for Immunocompromised Patients**

IC Condition	ICD-10 Code
HIV/AIDS*	B20-B24
Solid malignancy	
Organ/system malignant tumors	C00-C07; C11-C19; C22-C80; Z85
Neuroendocrine tumors	C7A; C7B; D3A
Neoplasms of uncertain behavior	D00-D49
Bone marrow transplant	Z94.81
Organ transplant	
Complications of transplanted organ	T86
Organ transplant status	Z94 except Z94.81; Z98.85
Rheumatologic or other inflammatory condition	
Sarcoidosis	D86
Amyloidosis Not Otherwise Specified (NOS)	E85
Familial Mediterranean fever	E85.0; M04
Amyloidosis Not Elsewhere Classified (NEC)	E85.1; E85.3; E85.8
Multiple sclerosis	G35
Other Central Nervous System (CNS) demyelination	G36; G37.1; G37.3; G37.8; G37.9
Acute infective polyneuritis	G61.0; G61.9
Acute myocarditis	I40
Polyarteritis nodosa and other	M30
Allergic alveolitis/pneumonitis NOS	T78.40; J67.9
Other alveolar pneumonopathy	J84.01; J84.02; J84.09
Enteritis and colitis	K50-K52

PFIZER CONFIDENTIAL

CT24-WI-GL02-RF02 4.0 Non-Interventional Study Protocol Template For Secondary Data Collection Study

15-Jun-2022

Page 38 of 41

IC Condition	ICD-10 Code
Lupus erythematosus	L93.0; L93.2; M32
Diffuse connective tissue disease	L94; M35.8; M35.9
Arthropathy with infection	M12.9; M01.X0; M02.10
Crystal arthropathies	M11
Rheumatoid arthritis/inflammatory polyarthropathy	M05-M14
Inflammatory spondylopathies	M46
Polymyalgia rheumatica	M31.5; M35.3
Chronic inflammatory demyelinating polyneuropathy	G61.81
Immune thrombocytopenic purpura	D69.3
Primary Immunodeficiency	
X-linked agammaglobulinemia	D80.8
Common variable immunodeficiency	D83.1; D83.2; D83.8; D83.9
Immunoglobulin A (IgA) deficiency	D80.2
Immunoglobulin G (IgG) sub-class deficiency	D80.3
Severe combined immunodeficiency	D81.1
Di George syndrome	D82.1
Wiskott-Aldrich	D82.0
Ataxia telangiectasia	G11.3
Interferon-gamma/Interleukin 12 axis deficiencies	D84.89
Persistent complement, properdin or Factor B deficiency	D84.1
Received eculizumab for >14 days in the baseline period	
Chronic granulomatous disease	D71
Chediak-Higashi	E70.330
Leukocyte adhesion deficiency	D72: Genetic anomalies of leukocytes
Myeloperoxidase deficiency	D72.89: Other specific disorders of White Blood Cells (WBCs)
Other immune conditions	
Disorders of immune mechanism	D89
Neutropenia	D70
Functional disorders of neutrophils	D71

IC Condition	ICD-10 Code
Genetic anomalies of leukocytes	D72.0
Decreased leukocyte count	D72.81
Leukocyte disease NEC	D72.89
Leukocyte disease NOS	D72.9
Myelofibrosis	D75.81
Blood diseases NEC	D47.4; D75.89; D75.9; D89.2
Blood diseases NOS	D75.9; D75.89
Immunologic findings NEC	R76; R83.4-R87.4; R89.4
Nonspecific immune findings NEC and NOS	R76; R83.4-R87.4; R89.4
Sickle cell disease	D57
Asplenia	Q89.01
Psoriatic arthritis	L40.52
Kidney condition	
Chronic kidney disease	A18.11; A52.75; B52.0; C64.x; C68.9; D30.0x; D41.0x-D41.2x; D59.3; E08.2x; E09.2x; E10.2x; E10.65; E11.2x; E11.65; E13.2x; E74.8; I12.xx; I13.0; I13.1x; I13.2; K76.7; M10.3x; M32.14; M32.15; N01.x-N08.x; N13.1; N13.1x-N13.39; N14.x; N15.0; N15.8; N15.9; N16; N17.x; N18.1-N18.5; N18.8; N18.9; N19; N25.xx; N26.1; N26.9; O10.4xx; O12.xx; O26.83x; O90.89; Q61.02; Q61.1x-Q61.8; Q26.0-Q26.39; R94.4
End stage renal disease	N18.6 AND on dialysis (any type): Z99.2; Z49; Z9115; Z4931; OR Z4901
On hemodialysis	Any participant with the ESRD codes above and ≥1 hemodialysis procedure session during the baseline period identified by at ≥1 of the following codes: Z49.31; Z49.32; I953; A4680; A4690; A4706-A4709; A4730; A4740; A4750; A4755; A4802; A4870; A4890; A4918; E1520; E1530; E1540; E1550; E1560; E1575; E1580; E1590; E1600; E1610; E1615; E1620; E1625; E1636; G0365; G0392; G0393; G8081; G8082; G8085; S9335; 90935; 90937; 90940; 93990; 36800; 36810; 36815
On peritoneal dialysis	Any participant with the ESRD codes above and ≥1 peritoneal dialysis procedure session during the baseline period identified by ≥1 of the following codes: Z49.02; 90945; 90947
Hematologic malignancy**	

IC Condition	ICD-10 Code
Lymphatic and hematopoietic tissue malignancy	C81-C83; C88-C96

CNS: central nervous system; ICD-10: International Classification of Diseases, 10th Revision; IgG: Immunoglobulin G, IgA: Immunoglobulin A, NOS: not otherwise specified; NEC: necrotizing enterocolitis; WBCs: White blood cells.

\*Excluded asymptomatic HIV code of ICD-10: Z21.

\*\*Required to have usage of an immunosuppressive medication (chemotherapeutic agent, immunomodulator, or systemic corticosteroids) for >14 days anytime during the baseline period.

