## 9.7. Data Analysis

Detailed methodology for summary and statistical analyses of data collected in this study will be documented in a statistical analysis plan (SAP), which will be dated, filed, and maintained by the sponsor. The SAP may modify the plans outlined in the protocol; any major modifications of primary endpoint definitions or their analyses would be reflected in a protocol amendment.

A separate statistical analysis plan will provide analysis and programming details along with detailed table shells. A sample of the table of results expected from the primary aim of this descriptive study is listed in [Table 8](#).

All descriptive statistics will be presented as n, % for the categorical variables, or mean  $\pm$  SD, median (interquartile range) for the numerical (continuous variables), as appropriate.

Study sample will be stratified by age group: 18-29, 30-49, 50-64, 65-74,  $\geq$ 75. Numerical outcomes included the number of COVID-19 vaccines received, date of last vaccination, days from last COVID-19 vaccination to date of Paxlovid™ treatment (eg, Prescription and dispensing date), days from COVID-19 diagnosis to date of Paxlovid™ treatment (eg, dispensing date), days from COVID-19 symptom onset to date of Paxlovid™ treatment (eg, dispensing date).

Categorical outcomes included comorbid conditions and COVID-19 therapy. Possible comorbid conditions include obesity (BMI  $\geq$  30), chronic kidney disease, diabetes mellitus, primary and Secondary Immunosuppressive disease or immunosuppressive treatment, cardiovascular disease (including congenital heart disease) or hypertension, active immunosuppressive disease (such as lymphoma, leukemia, etc.), active Immunosuppressive treatment (Chemo, Steroids, etc.) (Immunocompromised, defined in [ANNEX 2](#). **IMMUNOCOMPROMISED ICD-10 CODE LIST**).

WHO guidelines on COVID-19 therapeutics include the following groups

- **High risk:** people who are immunosuppressed; estimated hospitalization rate of 6%.
- **Moderate risk:** >65 years of age, conditions like obesity, diabetes and/or chronic conditions including chronic obstructive pulmonary disease, kidney or liver disease, cancer, with disabilities, and with comorbidities of chronic disease; estimated hospitalization rate of 3%.

- **Low risk:** those who are not in the high or moderate risk categories; low risk of hospitalization (0.5%) – most people are low risk.

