	

• Immunocompromised state: Solid malignancy

• Immunocompromised state: Bone marrow transplant

• Immunocompromised state: Organ transplant

• Immunocompromised state: Rheumatologic/inflammatory

• Immunocompromised state: Primary immunodeficiency

• Immunocompromised state: Other immune conditions

• Immunocompromised state: CKD or ESRD

• Immunocompromised state: Hematologic malignancy

• Immunocompromised state: IS drug only

• Immunocompromised state: Anti-metabolites

• Immunocompromised state: >1 IC condition

• Mental health conditions (mood disorders, including depression, and schizophrenia spectrum disorders)

• Overweight and obesity

• Pregnancy and recent pregnancy (for at least 42 days following end of pregnancy)

• Sickle cell disease (SCD) or thalassemia

• Smoking, current or former

• Solid organ or blood stem cell transplant (includes bone marrow transplants)

• Stroke or cerebrovascular disease

• Peripheral vascular disease

• Transient Ischemic Attack

• Substance use disorders (alcohol, opioid, or cocaine use disorder)

• Tuberculosis

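### Protocol Table 9 codes neoplasms of uncertain behavior as D00-D49, a range that also takes in in-situ and benign neoplasms, so patients can be flagged immunocompromised for a benign tumor

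*Protocol*

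**What the plan says.** Annex 3 of the protocol identifies a participant as immunocompromised by diagnosis after at least one hospitalization, or at least two "outpatient visits on separate dates with an ICD-10-CM code on a healthcare claim indicating an IC condition", within the 12-month baseline. Use of listed immunosuppressive drugs is an alternative route. Table 9 supplies the codes.

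Under its solid malignancy heading, Table 9 has a row for "Neoplasms of uncertain behavior" coded D00-D49. No medication condition is attached to that heading or its rows. The footnote that reads "Required to have usage of an immunosuppressive medication (chemotherapeutic agent, immunomodulator, or systemic corticosteroids", with a minimum of more than 14 days, is tied to hematologic malignancy only.

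Protocol Table 6 carries a reporting category "Immunocompromised state: Solid malignancy" and another for patients with more than one immunocompromising condition. Section 9.7 sends the reader to the code list for the immunocompromised comorbidity (it cites Annex 2, but the list is printed as Annex 3). Section 9.7 then describes the WHO risk groups separately. High risk is "people who are immunosuppressed; estimated hospitalization rate of 6" percent, with no pointer to Table 9, and cancer is placed in the moderate-risk group. The SAP repeats the WHO groups and contains no immunocompromised code list.

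**The concern.** The row label and its code range do not describe the same patients. Anyone applying the table as written would put a benign tumor, such as a uterine fibroid (D25) or a lipoma (D17), under solid malignancy and hence among the immunocompromised once the visit rule is met. Confirmed hematologic cancer, by contrast, must also pass a medication test.

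Describing pre-existing comorbidities is the primary objective, so the affected percentages are main results. Comorbidities are also among the characteristics the SAP lists for propensity-score selection of controls, so a misclassified flag could enter the matching as well.

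**Working it through.** The plan states no figure on this point, so there is nothing to reproduce. The check has three parts.

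**1. Label against range.** Annex 3 names ICD-10-CM but does not print its block titles; I take them from that classification: D00-D09 in situ, D10-D36 benign, D37-D48 uncertain behavior, D49 unspecified. D00 to D49 holds 50 two-digit categories. The label fits D37 to D48, which is 12 of 50 (24%). The other 38 of 50 (76%) lie outside it. These are counts of categories, not of patients.

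**2. Range against the rest of Table 9.** This part needs only the protocol.
- D3A is listed on the neuroendocrine tumor row, under the same solid malignancy heading.
- "D30.0x; D41.0x-D41.2x" are listed under chronic kidney disease.
- D47.4 is listed under blood diseases, in the string "D47.4; D75.89; D75.9; D89.2".

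All of these fall inside D00-D49. The kidney and blood codes therefore sit under two immunocompromising conditions at once, and one such code could place a patient in the Table 6 category for more than one condition. D3A is repeated within a single heading, so it does not have that effect.

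**3. Illustration of size.** Inputs: N = 8263 (protocol section 9.5); t, the share truly immunocompromised, and p, the share of the remainder with a qualifying benign or in-situ code. Both t and p are assumptions.

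- True cases T = N × t
- False flags F = N × (1 − t) × p
- Relative inflation = F / T
- Share of flagged patients who are true cases = T / (T + F)

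At t = 5%: T = 8263 × 0.05 = 413. With p = 1%, F = 8263 × 0.95 × 0.01 = 78. With p = 5%, F = 8263 × 0.95 × 0.05 = 392.

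| t | T | F, p = 1% to 5% | F / T | T / (T + F) |
|---|---|---|---|---|
| 3% | 248 | 80 to 401 | 32% to 162% | 75.6% to 38.2% |
| 5% | 413 | 78 to 392 | 19% to 95% | 84.0% to 51.3% |
| 10% | 826 | 74 to 372 | 9% to 45% | 91.7% to 69.0% |

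At a given p, the number of false flags hardly depends on t, whereas the relative inflation depends on it heavily.

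**The case against.** **Table 9 may not drive the analysis.** The SAP has no such code list, and its shells show a general ICD-10 comorbidity line and an immunosuppression risk-factor line, not a solid-malignancy category. Data are abstracted by people from unstructured charts, and a reviewer might not flag a lipoma. Protocol Table 6 also lists cancer separately, without tying it to Table 9. This limits how surely the error reaches a printed table, and it means that inflation of the separate cancer line is not established. It does not remove the defect: section 9.7 still directs the immunocompromised variable to this list, the Annex 3 rule is based on codes, and the SAP does not replace it.

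**The block meanings are not in the documents.** True, and the overlaps in part 2 show duplication rather than benign content. But Table 9 cannot be applied without the classification it names, so the mismatch can be confirmed in the source the programmer must use.

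**The size is assumed.** This stands in full. Table 9 also counts chronic kidney disease and many other conditions, so the true share under its own rule may be well above 5%.

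**Stronger readings that the documents do not support:**
- A reader might infer that these patients also move into WHO high risk and so into the strongly recommended group. Neither document says that Table 9 defines immunosuppressed for that purpose, and the WHO text puts cancer itself at moderate risk. The inference is tempting because Table 9 is the only operational definition of immunocompromised available.
- A reader might infer that every patient with a fibroid, lipoma or polyp is counted. The visit rule must be met, and only polyps coded within the range qualify.
- A reader might see the same fault in the row "Sickle cell disease", coded D57. Nothing in the documents contradicts that row, so it is not part of this point.

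**Conclusion.** The row is miscoded for its label. Applied as written, Table 9 can flag patients with benign or in-situ neoplasms as immunocompromised through solid malignancy, which inflates a descriptor under the primary objective. It also lets some single codes count as two conditions. The mismatch rests on the ICD-10-CM block structure; the duplication is visible in the protocol alone.

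The size cannot be known from the documents. The 78 to 392 false flags hold only under the stated assumptions (5% truly immunocompromised, 1-5% of the rest with a qualifying code), and no percentage inflation should be quoted as a finding. Any effect on the WHO high-risk count is conditional on a use of Table 9 that the documents do not state.

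**What to change.** - On this row of Table 9, replace D00-D49 with D37-D48. State explicitly whether D49 is kept, with a label that fits it. If in-situ disease is wanted, give it its own labelled row with a reason.
- Assign each duplicated code to one condition. Narrowing the row takes D30.0x out of it, but D41.0x-D41.2x and D47.4 lie within D37-D48 and need a separate decision. Say that D3A belongs to the neuroendocrine row only.
- In the SAP, give or cite the final code list and state whether it defines immunosuppressed for the WHO groups. If it does not, give the definition that does.

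This is an edit to a code list and a short SAP statement, made before programming, with no new data. The downside is a smaller immunocompromised count.

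### Protocol Table 9, chronic kidney disease row: two diabetes codes outside the kidney pattern, N17.x and an out-of-order Q26 range let in patients without chronic kidney disease, while N18.6 as the sole kidney code is lost

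*Protocol*

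**What the plan says.** Annex 3 of the protocol classes a participant as immunocompromised if a Table 9 code is recorded at one or more hospitalizations, or at two or more outpatient visits on different days, in the 12-month baseline. Use of certain immunosuppressive drugs is an alternative route. The code set named is ICD-10-CM.

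Under the kidney heading of Table 9:

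- The chronic kidney disease row includes the run "D59.3; E08.2x; E09.2x; E10.2x; E10.65; E11.2x; E11.65; E13.2x; E74.8", in which the E08 to E13 entries are the diabetes codes.
- The same row includes "N15.9; N16; N17.x; N18.1-N18.5; N18.8; N18.9; N19". N18.6 is not among them.
- The row ends with "Q61.02; Q61.1x-Q61.8; Q26.0-Q26.39; R94.4".
- The end-stage row reads "N18.6 AND on dialysis (any type): Z99.2; Z49; Z9115; Z4931; OR Z4901". The hemodialysis and peritoneal dialysis rows below it each start from the end-stage codes and add a procedure code.

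Protocol Table 6 (Annex 2) carries the sub-category "Immunocompromised state: CKD or ESRD". It also lists diabetes and chronic kidney disease, the latter at any stage, as comorbidities in their own right. Protocol Section 9.7 points to the code list as the definition of immunocompromised, although it cites Annex 2 and the list is in Annex 3. The SAP neither reproduces nor cites Table 9.

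**The concern.** A code list is applied literally by the programmer. If the kidney row contains codes that are not chronic kidney disease, patients are counted in the wrong category and nothing in the output shows it. The .65 entries matter most. Diabetes is one of the criteria for being offered Paxlovid (SAP, Study population), so diabetics are likely to be common in this cohort, and a glucose-control code is not evidence of kidney disease or of immune compromise.

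The direct stake is the primary objective, the description of baseline clinical characteristics: the immunocompromised count and its kidney sub-category would be inflated. In the other direction, leaving out patients who carry only the end-stage code is odd when N18.5 counts unconditionally.

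**Working it through.** The documents give no figure on this point, so there is none to reproduce. The check sets codes against the row as printed, then shows a range for the size.

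**Step 1: which codes the row accepts.** Reading x as any character and expanding the ranges, the chronic kidney disease row has 48 entries. Test codes give:

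| Code | Chronic kidney disease row |
|---|---|
| E11.22 | accepted (E11.2x) |
| E10.65, E11.65 | accepted (listed by name) |
| E08.65, E09.65, E13.65 | not accepted |
| E11.9 | not accepted |
| N17.9 | accepted (N17.x) |
| N18.5 | accepted (N18.1-N18.5) |
| N18.6 | not accepted |
| I12.0, I13.11, I13.2 | accepted |
| Q26.0, Q26.2 | accepted |
| Q62.0 | not accepted |

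The .2x pattern is used for E08, E09, E10, E11 and E13; the .65 code is added for E10 and E11 only. Q26 comes after Q61 and before R94 in a list that otherwise ascends.

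**Step 2: what the codes mean.** The documents do not print these meanings. In ICD-10-CM, the set that Annex 3 names, .65 is diabetes with hyperglycemia, N17 is acute kidney failure and Q26 is malformation of the great veins. For .65 and Q26 the pattern break and the order break point the same way. N17.x has no such internal sign and rests on the code set alone. For N18.6 the label is in Table 9 itself: end-stage renal disease.

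**Step 3: consequence under the Annex 3 rule.**

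- Only listed code is E10.65 or E11.65, at one admission or two outpatient visits: immunocompromised through the kidney row.
- Only kidney code is N18.6, with no dialysis code: fails the chronic kidney disease row (code absent), the end-stage row (needs a dialysis Z-code) and both dialysis rows (need a dialysis code as well). The patient is in no kidney row.
- N18.6 together with a listed I12 or I13 code or a diabetic .2x code: still captured by the chronic kidney disease row.

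**Step 4: size, by assumption only.** Let q be the share of the cohort that qualifies solely through E10.65 or E11.65. The documents give no value for q; 1% to 20% is assumed. N = 8263 (Protocol Section 9.5). Mislabelled patients = N × q:

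- 8263 × 0.01 = 83
- 8263 × 0.05 = 413
- 8263 × 0.10 = 826
- 8263 × 0.20 = 1653

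If only the roughly 3000 treated and 1000 untreated patients are analysed, the ends of the range are 4000 × 0.01 = 40 and 4000 × 0.20 = 800.

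**Step 5: dilution, only if Table 9 is used to define the WHO high-risk group.** Section 9.7 gives hospitalization rates of 6% (immunosuppressed) and 3% (moderate risk, which includes diabetes). Assume a share t = 5% is otherwise immunocompromised at 6% and the added diabetics are at 3%. The expected rate in the labelled group is (t × 6% + q × 3%) / (t + q):

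- q = 1%: (0.05 × 6% + 0.01 × 3%) / 0.06 = 5.50%
- q = 5%: (0.05 × 6% + 0.05 × 3%) / 0.10 = 4.50%
- q = 10%: (0.05 × 6% + 0.10 × 3%) / 0.15 = 4.00%
- q = 20%: (0.05 × 6% + 0.20 × 3%) / 0.25 = 3.60%

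At q = 10%, taking t as 2% or 10% gives 3.50% or 4.50%.

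**The case against.** The strongest objection is that the code meanings are not in the documents, which show only a pattern break and an ordering break. That would support a query but not a finding of error. It stands in part: a coder should confirm each entry, and N17.x has no internal sign against it. But the protocol makes ICD-10-CM its operating definition, and the internal signs agree with it for .65 and Q26. The N18.6 gap can be read from Table 9 alone.

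Four stronger readings are tempting, and the documents do not support them:

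- *End-stage disease without a dialysis code is dropped.* This is too broad. The row still admits such patients through I12.xx, the listed I13 codes, the diabetic .2x codes or another listed N18 code. Only those with N18.6 as the sole kidney code are lost.
- *Diabetics move from the WHO moderate-risk to the high-risk group, and from conditional to strong recommendation.* The WHO bullets in Section 9.7 do not cite Table 9, and neither document explicitly equates the risk tiers with the recommendation strengths. If Table 9 were used this way, the whole kidney block would be affected, because Section 9.7 places kidney disease at moderate risk; correcting the .65 codes would not cure that.
- *Diabetes and kidney disease can no longer be described separately.* Table 6 lists them as separate variables, and nothing states that Table 9 defines the kidney comorbidity. Protocol Table 3 and the SAP state the kidney risk factor with an eGFR criterion.
- *Q26 is a transposed Q62.* This is likely from its position but unconfirmed.

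Two further points stand. The protocol describes the record both as claims data (Section 9.4) and as unstructured charts abstracted into a case report form (Section 9.6), so it is unclear how completely codes will be available. And removing N17.x while leaving other broad entries, such as C64.x or R94.4, could look selective, which is a reason to have the whole row checked.

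**Conclusion.** The point holds as a set of specific errors in one row of Table 9. Applied as written, the row labels a patient with only E10.65 or E11.65 as immunocompromised through kidney disease, admits N17.x and an out-of-place Q26 range, and leaves out a patient whose sole kidney code is N18.6 without a dialysis code, although Table 6 counts kidney disease at any stage.

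The .65 codes carry most of the weight. The range of 83-1653 patients follows from an assumed 1-20% and from nothing in the documents; it counts only patients with no other route to immunocompromised status. The N17, Q26 and N18.6 effects are probably small. Any effect on the WHO risk split is conditional on a use of Table 9 that the documents do not state. Whether kidney disease belongs under immune compromise at all is a separate question; these corrections are needed whichever way it is settled. The change should be made before programming, because it is cheap and the misclassification would not be visible in the tables.

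**What to change.** In the chronic kidney disease row of Protocol Table 9:

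- Remove E10.65, E11.65 and N17.x.
- Check Q26.0-Q26.39 against the list from which the row was taken, and correct or delete it. Do not substitute Q62 without that check.
- Let N18.6 count without a dialysis code, and keep the end-stage and dialysis rows as sub-categories.

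Have a coder check the whole row against ICD-10-CM at the same time. State in the SAP whether Table 9 defines the immunosuppressed group for the WHO comparison, and correct the annex reference in Protocol Section 9.7.

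The cost is a code-list edit and a short SAP statement before programming, with no new data. Removing the .65 and N17 codes lowers the kidney and immunocompromised counts, while admitting N18.6 alone raises them slightly.

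### Protocol Table 9 leaves unexplained gaps in its malignancy code ranges and lists some codes under two immunocompromising conditions; the gaps can affect the immunocompromised flag, the double listings only the condition-level counts.

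*Protocol*

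**What the plan says.** Protocol section 9.7 lists "active immunosuppressive disease (such as lymphoma, leukemia, etc" among the comorbid conditions and points by title to the immunocompromised code list, which is Annex 3, Table 9. Annex 3 flags a patient on at least one hospitalization, or at least two outpatient visits on separate dates, carrying a listed code. Use of specific immunosuppressive drugs in the 12-month baseline period also qualifies.

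In Table 9:
- The organ/system tumor row under solid malignancy reads "C00-C07; C11-C19; C22-C80; Z85".
- The hematologic malignancy row reads "C81-C83; C88-C96". Its footnote also requires more than 14 days of an immunosuppressive medication in the baseline period.
- The chronic kidney disease row begins "A18.11; A52.75; B52.0; C64.x; C68.9; D30.0x; D41.0x-D41.2x" and later includes M10.3x, M32.14 and M32.15.
- The primary immunodeficiency group has "Chronic granulomatous disease D71" and, for myeloperoxidase deficiency, "D72.89: Other specific disorders of White Blood Cells (WBCs". The group for other immune conditions has "Functional disorders of neutrophils D71" and lists D72.89 again.

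Protocol Table 6 reports solid malignancy, hematologic malignancy, rheumatologic/inflammatory disease, primary immunodeficiency, other immune conditions, CKD or ESRD, and immunosuppressive drug only as separate states. It adds "Immunocompromised state: >1 IC condition". The SAP neither restates nor corrects the list.

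**The concern.** A code list is programmed literally. A category missing from a range is not picked up, and a code printed in two groups is counted in both unless a rule says otherwise.

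The gaps bear on who is immunocompromised. That is a baseline characteristic under the primary objective. Section 9.7 also makes immunosuppression the criterion for the WHO high-risk group, which feeds the first secondary objective and SAP Table 8. The double listings bear on how many immunocompromising conditions a patient is said to have, and on the size of each condition group.

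The list states its deliberate departures elsewhere: footnotes exclude Z21 and add the medication requirement for hematologic malignancy. Silence on the gaps therefore suggests an oversight.

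**Working it through.** No figure in the plan has to be reproduced. The check is on coverage and overlap of the printed codes.

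**1. Coverage of C00-C96 (97 three-character categories)**
- Solid-tumor row, C00-C80, 81 categories. Listed: C00-C07 (8) + C11-C19 (9) + C22-C80 (59) = 76. Missing: 81 − 76 = 5, namely C08, C09, C10, C20 and C21.
- Hematologic row, C81-C96, 16 categories. Listed: C81-C83 (3) + C88-C96 (9) = 12. Missing: 16 − 12 = 4, namely C84, C85, C86 and C87.
- No other row supplies any of these. C87 is set aside, because the documents do not show that it holds a diagnosis. That leaves 5 + 3 = 8 categories at issue.

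**2. Codes in two condition groups**

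| Groups | Codes | Count |
|---|---|---|
| Primary immunodeficiency; other immune conditions | D71, D72.89 | 2 |
| Solid malignancy; kidney | C64.x, C68.9 (inside C22-C80); D30.0x, D41.0x, D41.1x, D41.2x (inside D00-D49) | 6 |
| Rheumatologic; kidney | M10.3x (inside M05-M14); M32.14, M32.15 (inside M32) | 3 |
| Solid malignancy; other immune conditions | D47.4 (inside D00-D49) | 1 |

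Total: 2 + 6 + 3 + 1 = 12. The leukocyte adhesion deficiency row adds an ambiguous D72 entry. If it means D72.0, which its label matches, the total is 12 + 1 = 13. If it means the whole category, D72.0, D72.81 and D72.9 all overlap and the total is 12 + 3 = 15. A few code lists (transplant status, dialysis procedures, parts of the O, Q, N13 and R83-R87 ranges) were not compared pairwise, which can only understate the overlap.

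**3. What each defect does to the flag**
- *Omitted solid-tumor codes.* This row carries no medication requirement. A patient whose only qualifying evidence is one of these codes is not flagged. Section 9.7 lists cancer under moderate risk, so such a patient would be placed there (quoted hospitalization rate 3%) instead of in the high-risk group (6%).
- *Omitted lymphatic codes.* Under a completed row the patient would still need more than 14 days of immunosuppressive medication. Such a patient may already enter through the medication route, but under the drug-only state and not as hematologic malignancy.
- *Double-listed codes.* The flag is met if any row is met, so a second listing adds nothing to it. The condition count does change: encounters that qualify a patient on C64.x satisfy both the solid malignancy and the kidney definitions, and one diagnosis can then meet "Immunocompromised state: >1 IC condition".

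**The case against.** The strongest reply is that the practical effect is small.

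- *Lymphoma.* A reader might infer that every patient with an omitted lymphoma code is classed as not immunocompromised. The documents do not support that, given the medication footnote and the separate medication route. How many keep the flag depends on the drug list that Annex 3 announces. That list is not in the text available for this review, and its absence is not held against the plan. What stands is the wrong sub-label and a possible loss of the flag.
- *Overlaps and the WHO groups.* A reader might infer that double listing inflates the WHO high-risk count. It cannot, because the yes/no flag is unaffected.
- *The more-than-one-condition count.* No SAP table shell prints it; the shells have one combined immunosuppression row and an undivided comorbidity line. Nor does either document give a counting algorithm, so it is too strong to say that every patient coded C64.x will be counted twice. But the protocol specifies the variable and gives no hierarchy or de-duplication rule, so nothing prevents it.
- *Deliberate listing.* M32.14 and M32.15 may be meant for both lupus and kidney disease. That is possible, and a stated counting rule would settle it.
- *Other capture.* Table 6 has a separate cancer variable, and charts are reviewed by people. This limits the loss of cancer as a comorbidity. It does not repair the immunocompromised definition, which rests on the codes and drugs in Annex 3.

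**Conclusion.** The point holds as a defect in one code list. Eight malignancy categories (C08-C10, C20-C21, C84-C86) are omitted without explanation. The omission can lower the immunocompromised count and, through it, the WHO high-risk count; the direct route is the five solid-tumor categories. Between 12 and 15 codes or stems sit in two groups, depending on how D72 is read. This distorts condition-level counts only.

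The conclusion rests on three assumptions. First, C84-C86 are lymphatic malignancies; the documents do not print their names, but the row label and their place between C83 and C88 imply it. Second, the WHO criterion of immunosuppression will be programmed from the Annex 3 flag; section 9.7 suggests this but does not say so outright. Third, programmers will use Table 9 as printed.

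The number of patients affected cannot be computed, because the documents give no code frequencies. The counts above are of code categories and do not measure bias. A reader might also equate WHO high risk with the strongly recommended category; sections 9.3 and 9.7 name both schemes without printing that mapping, so the point goes no further than the high-risk count.

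**What to change.** Before programming:

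1. Add C08-C10 and C20-C21 to the solid-tumor row and C84-C86 to the hematologic row, or give a reason in a footnote for each category left out.
2. Either assign each code to one condition group or state a hierarchy, so that a single code cannot by itself satisfy "Immunocompromised state: >1 IC condition". Either convention works, and which group takes which code is the sponsor's choice.
3. State whether the D72 entry means the whole category or D72.0.
4. State that the WHO immunosuppression criterion is derived from this flag, if that is the intention.

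The cost is an edit to one table and a sentence or two of derivation rules, with no new data. Section 9.7 lets the SAP modify the protocol's plans, so the corrected list can go there. The sponsor should decide whether the change is a major modification of a primary endpoint definition, which that section would route to a protocol amendment.
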